8.1.2 Propensity score analysis

Propensity scores will be calculated for each patient using all collected, potentially confounding variables (analogous to Section 4.1). These variables include (but are not limited to) the following Baseline characteristics:

- Age
- Gender
- Race
- Smoking status
- Other biologic treatment use in the year prior to Baseline
- Immunosuppressant use in the year prior to Baseline
- Corticosteroid use in the year prior to Baseline
- Disease extent
- Diagnosed with fistulas
- Duration of disease
- Physician assessment of disease severity
- Number of Crohn’s related hospitalizations in the year prior to Baseline
- Number of surgical resections in the year prior to Baseline
- Calendar year of enrollment

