4.8.1 Enrollment Visit

For each patient enrolled in this registry, the Investigator will document the following information into the corresponding eCRFs within the registry study EDC system:

- Demographic information such as gender, age, race, ethnicity, household income, occupation and smoking status
- Crohn's disease history, including length of time since initial presentation of symptoms, date of diagnosis, all past treatment and surgeries for CD (with special focus on anti-TNF α and other biologics), and reason for switch to Cimzia or other medications since diagnosis and within the past 3 months
- Investigator's assessment of CD severity
- Investigator's completion of the Harvey-Bradshaw Index (HBI) – See Section 12.1 APPENDIX A. This may also be completed by qualified site personnel as designated by the Investigator
- Patient's assessment of CD severity
- Patient's completion of the modified HBI. The modified HBI does not include the abdominal mass question contained in the full HBI

- Other medical history including current medical status, concomitant medications, and planned treatment period (if known) with special focus on previous occurrence of each AE of interest and related risk factors (eg, history of serious infections, conditions that might place a patient at higher risk of serious infection)

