3.2.1 Exposure

Cancer progresses in several stages before reaching a detectable, malignant state. While this latency period may differ by cancer type, it is generally believed to occur over a long period of time (3). Thus, a treatment-related event may not be seen until years after the initial exposure. In contrast, acute events typically have very short latency periods; therefore, it is unlikely that a treatment-related event will occur after exposure to the product has ended. For the primary endpoint analysis, 2 different methods of person time calculations will be used, one for malignancy events (Section 3.2.1.1) and one for acute events (Section 3.2.1.2).

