4 STATISTICAL/ANALYTICAL ISSUES

4.1 Adjustments for covariates

Conventional multiple regression analysis and propensity score analysis will include (but are not limited to) the following Baseline characteristics in the initial run of the model.

Characteristics that are continuous will remain as such. Categorical variables will use the values in parentheses:

- Age
- Gender (Male, Female)
- Race (American Indian/Alaskan native, Asian, Black, Native Hawaiian/Pacific Islander, White, Other/Mixed)
- Smoking status (Never, Current, Former)
- Other biologic treatment use in the year prior to Baseline (Yes, No)
- Immunosuppressant use in the year prior to Baseline (Yes, No)
- Corticosteroid use in the year prior to Baseline (Yes, No)
- Disease extent (Ileum, Colon, Illeocolon, Upper GI, Ileum + upper GI, Colon + upper GI, Illeocolon + upper GI, Other)
- Diagnosed with fistulas (Yes, No)
- Duration of disease
- Physician assessment of disease severity (Remission, Mild-moderate, Moderate-severe, Severe)
- Number of Crohn's related hospitalizations in the year prior to Baseline
- Number of surgical resections in the year prior to Baseline
- Calendar year of enrollment

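### The named adjustment set looks back only one year for Crohn's disease drugs and does not name prior malignancy, although the primary outcome is malignancy and both histories are collected

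*SAP*

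**What the plan says.** SAP 8.1.2 and SAP 4.1 name the same 14 baseline covariates. The three on drug history are "Other biologic treatment use in the year prior to Baseline", "Immunosuppressant use in the year prior to Baseline" and "Corticosteroid use in the year prior to Baseline"; SAP 4.1 codes each as yes or no. Protocol 6.4.1.3.1 uses the same one-year windows. None of the three lists names prior malignancy.

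All three lists are open-ended, and SAP 8.1.2 opens by promising to use every collected potential confounder. SAP 8.1.2.1 nevertheless says that the predictors are those listed in 8.1.2 and that they were chosen in advance with a directed acyclic graph. SAP 8.1.5 carries the same covariate vector into the conventional regression.

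On latency, SAP 3.2.1 says: "Thus, a treatment-related event may not be seen until years after the initial exposure". On data, Protocol 4.8.1 collects "all past treatment and surgeries for CD" and medical history with "special focus on previous occurrence of each AE of interest and related risk factors". Malignancy is one of those events of interest. SAP 6.2 uses medical history only for descriptive tables and puts Crohn's disease medication history in a listing. Neither eligibility section (Protocol 4.3, SAP 2.3.1) excludes patients with a prior cancer.

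**The concern.** A covariate should be measured over a period that matters for the outcome. The plan treats cancer latency as long enough to attribute every later malignancy to Cimzia after any exposure, including known use before enrollment (SAP 3.2.1.1). For the other drugs its covariates stop at one year. A patient who took an immunosuppressant for ten years and stopped 13 months before baseline gets the same value as a patient who never took one.

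Prior malignancy predicts later malignancy and may influence the choice of drug. The plan itself calls the events of interest known serious risks of the TNF-blocker class (Protocol 3), and Protocol 6.4.1.3 names past response to treatment as a driver of drug choice.

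If either history differs between cohorts after matching on the named variables, the matched sample can look balanced while the malignancy rate ratios and hazard ratios remain confounded. Prior serious infection raises the same question for the serious-infection contrast.

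**Working it through.** No figure in the plan depends on this choice, so there is none to reproduce. The check has two parts.

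**1. Lists against data collected**

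| Item | Collected at enrollment? | Named in SAP 4.1 / 8.1.2? |
|---|---|---|
| Drug use within one year of baseline | Yes | Yes, three yes/no indicators |
| Drug use more than one year before baseline | Yes (Protocol 4.8.1) | No |
| Prior malignancy | Yes (Protocol 4.8.1) | No |
| Prior serious infection | Yes (Protocol 4.8.1) | No |

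Other planned steps do not fill the gap. The balance checks in SAP 8.1.2.4 concern measured covariates. The iterative refinement in SAP 8.1.2.3 mentions interactions and polynomial terms, not new variables. The conventional regression shares the omission. Protocol 6.4.1.3.2 promises sensitivity analyses for hypothetical confounding, but the SAP describes none.

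**2. Possible size**

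For one omitted binary confounder, the observed ratio is the true ratio multiplied by

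B = [1 + p1(R − 1)] / [1 + p0(R − 1)],

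where p1 and p0 are its prevalences in Cimzia and comparator, and R is its risk ratio for the outcome. The documents give none of these inputs; all are assumed.

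| Omitted variable | p1 | p0 | R | B |
|---|---|---|---|---|
| Prior malignancy | 0.02 | 0.05 | 2 | 1.02/1.05 = 0.971 |
| Prior malignancy | 0.02 | 0.05 | 4 | 1.06/1.15 = 0.922 |
| Earlier drug exposure | 0.70 | 0.50 | 1.3 | 1.21/1.15 = 1.052 |
| Earlier drug exposure | 0.70 | 0.50 | 2 | 1.70/1.50 = 1.133 |
| Earlier drug exposure, wider | 0.60 | 0.40 | 3 | 2.20/1.80 = 1.222 |
| Earlier drug exposure, wider | 0.80 | 0.50 | 3 | 2.60/2.00 = 1.300 |

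Swapping p1 and p0 inverts B: 1.133 becomes 0.882 and 1.300 becomes 0.769. With p1 = p0, B = 1 and there is no bias.

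For scale only, SAP 2.4 gives 1.56 as the detectable rate ratio for solid malignancies. On the log scale, 1.133 is ln 1.133 / ln 1.56 = 0.125/0.445 = 28% of that ratio, and 1.300 is 0.262/0.445 = 59%.

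A prevalence of 2% against 5% gives a standardized difference of 0.03/√{0.5[(0.02)(0.98) + (0.05)(0.95)]} = 0.03/0.183 = 0.164 in absolute value, below the 0.2 that SAP 8.1.2.4 calls imbalance. Adding prior malignancy to the balance table alone would therefore not ensure adjustment; it has to be in the model.

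**The case against.** The strongest reply is that the plan already allows for this. The lists are open, SAP 4.1 describes its set as the one for the initial model run, and SAP 8.1.2 promises all collected confounders. That stands: a reader might infer that the plan bars these variables, and it does not. They are simply not pre-specified, and SAP 8.1.2.1 leaves unclear whether the list is open or fixed. The graph behind the selection is not in the documents, so a reasoned omission cannot be ruled out.

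Three other stronger readings also fail:

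- **Recurrences count as events.** This is unsettled. SAP 3.6 counts events from consent and SAP 8.1.4 counts the first event in the study, which would include a recurrence. SAP 8.2.2 limits study-emergent events to those that first occur, or become more related to treatment, after the first post-enrollment dose, which may exclude it.
- **Prescribers steer patients with prior cancer away from Cimzia, so the bias hides risk.** The comparator includes other anti-TNF drugs (SAP 3.6). A class-level concern separates the cohorts only as far as comparator patients take other classes, and that share is not given.
- **Every history must be added.** Family history is not shown to affect drug choice and is at most a precision variable. Own-event history for all 16 rows of SAP Table 8.1 would be sparse and could require separate matched sets. Protocol 4.8.1 does not say that dates of past treatment are recorded, so cumulative duration may not be available.

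It is also fair that disease duration, fistulas, severity and recent drug use may partly stand in for earlier treatment, that SAP 6.2 would show a recorded imbalance in medical history, and that all analyses are descriptive. None of this replaces adjustment: the plan still reports hazard ratios and rate ratios with intervals, and confounding distorts these whether or not a hypothesis is tested.

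**Conclusion.** The point holds as a gap in pre-specification. The named set uses a one-year drug history and no cancer history for an outcome that the SAP describes as slow to appear, and the planned regression check repeats the gap.

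Whether it biases this study, and in which direction, cannot be determined from the documents. Under the assumed inputs, prior malignancy shifts the ratio by 3% to 8%. Earlier drug exposure shifts it by about 5% to 13%, and by up to about 30% under the widest assumptions. The prevalences in the formula should be read as differences that remain after conditioning on the named covariates; to the extent that those covariates act as proxies, the true shift is smaller. The two components may also act in opposite directions. The drug-history component is the more likely to matter beside a ratio of 1.56. This justifies a low-cost improvement and does not show that the planned comparison is invalid.

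**What to change.** 1. In SAP 4.1 and 8.1.2, add history of malignancy (yes/no).
2. In the same sections, add ever-use before baseline of biologics and of immunosuppressants, keeping the one-year indicators.
3. In the serious-infection model, add prior serious infection as a regression covariate, without building a separate matched set.
4. Repeat the malignancy rates and hazard ratios excluding patients with a pre-enrollment malignancy.
5. State whether a recurrence of a pre-enrollment cancer counts as an event, and reconcile SAP 3.6, 8.1.4 and 8.2.2 accordingly.

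If the graph gave a reason to leave out either history, stating that reason in SAP 8.1.2.1 would answer items 1 and 2. Family history, cumulative duration and own-event history for the rare outcomes are optional.

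The cost is SAP wording, recoding of baseline data already collected, a few more model terms and one repeated set of tables. The matched sample may lose a few pairs. No new data are needed.

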8.1.2.1 Propensity score estimation

The propensity score represents the probability that a specific patient receives Cimzia conditional on a set of known baseline confounding factors (4). A logistic regression model, with treatment cohort as the dependent variable, will be employed to estimate the conditional distribution of the treatment given the covariates. The predictors in this model are pre-treatment variables believed to be related to the study outcome of interest and are listed in Section 8.1.2 These variables were

selected a priori using a directed acyclic graph (DAG). This approach has the advantage of improving the statistical efficiency of a model. It also minimizes the introduction of bias which may result from more traditional confounder identification and adjustment approaches (5).

8.1.2.2 Overlap and Region of Common Support

Once the propensity scores are estimated, it is essential to investigate the validity or performance of these scores by verifying that sufficient overlap or common support of these scores exists between treatment cohorts. It is possible that some of the strata may contain only patients from either the Cimzia cohort or from the comparator cohort, which could lead to invalid comparisons. A necessary condition is that patients with the same covariate values have a positive probability of being assigned to either Cimzia or comparator, but with no perfect predictability (i.e. without a 0 or 1 probability). Thus, to ensure adequate performance of the propensity score, a common support region or a sufficient overlap of the distribution of the variables in Cimzia and comparator cohorts are needed. The common support region ensures that any combination of Baseline prognostic factors in the Cimzia cohort would also be observed in the comparator cohort. To evaluate adequate overlap of the propensity scores, several methods will be examined:

- Graphical method: A visual inspection of the density distribution of the propensity scores in both Cimzia and comparator cohorts will be performed (6). The extent of overlap should be evident from simple histograms or density distribution plots of the propensity scores from Cimzia and comparator cohorts. If the graphical representation shows a large disparity in propensity scores between the two cohorts, then covariates which are strong predictors of treatment will be examined to determine their confounding effects.
- Minima-Maxima Rule: The lower bound of the propensity scores will be determined as the larger of the minima of the scores in the 2 treatment groups while the upper bound will be computed as the smaller of the maxima. As an example, if Cimzia and the comparator propensity scores range from 0.01 to 0.8 and from 0.03 to 0.8, respectively, then the common region will be defined as [0.03, 0.8].
- Caliper method (matching): In order to obtain the largest sample possible from the entire patient enrollment, the size of the caliper will be set to a quarter of a standard deviation of the logit of the propensity score used as recommended by Rosenbaum and Rubin⁽⁷⁾.

Once an appropriate common support region is found, only non-discarded patients will be used in further propensity score analyses aimed at estimating treatment effects. Demographic and baseline characteristics of patients disregarded will be compared to those remaining in the analysis, and any difference detected between these two groups of patients will be taken into account in the interpretation of estimated treatment effects. Moreover, if these two groups of patients are found to be different with regards to baseline prognostic factors, the predicted probabilities generated from the propensity score model will be re-estimated on the reduced dataset determined by the common support region(8).

8.1.2.3 Propensity score matching

[figure not shown]
Propensity score matching will be used to construct a sample of patients which have similar covariate distributions between the Cimzia and comparator cohorts. A common sampling method known as the Mahalanobis metric matching with calipers will be implemented which will better balance the covariates between the cohorts. This method is

considered to be superior to other propensity score matching methods^(9,10).

The matching algorithm will proceed as follows. Propensity scores will be computed for each patient in the database using a logistic regression model with covariates as listed in Section 8.1.2 Cimzia patients will be randomly ordered, and the first Cimzia patient is selected. Comparator patients whose propensity score is within a given caliper are identified as an initial matched candidate to the Cimzia patient. Cimzia and comparator patients will be matched in a 1:1 ratio based on the smallest distance between propensity scores. If there is no comparator patient match, then this round of matching stops and the process continues with the next Cimzia patient. If there is only one match, then this match is considered final and the matched pair is removed from the pool and the process continues with the next Cimzia patient. If there are more than 2 comparator matches using a 1:1 ratio, then the Mahalanobis distances are recalculated based on a smaller set of key covariates and propensity score between the given Cimzia patient and those initially selected from the comparator cohort. The patient with the smallest distance from the given Cimzia patient is selected as the final matched candidate. The matched pair is then removed from the pool and the process repeats for the next Cimzia subject. All remaining comparator patients are available for the remaining matching rounds. The matching process continues until all Cimzia patients in the pool are exhausted.

This document cannot be used to support any marketing authorization application or any variations thereof.
REDACTED COPY

Diagram of the matching algorithm

To maximize the comparability of treatment cohorts, an iterative data-driven approach such as the one described by Rosenbaum and Rubin⁽¹¹⁾ will be adopted to develop the propensity score model. Terms in the model will include main effects, interactions, and nth-order ($n < 5$) polynomials. A buildup approach, starting with a simpler model, will be implemented. Comparability of treatment cohorts will be assessed after each iteration. If residual systemic differences are identified, the model will be re-parameterized until covariate balance is achieved or maintained within reasonable limits. If some differences persist, the variables in question will be controlled for in the regression model that assesses the effect of treatment cohorts on the risk of serious infections.

8.1.2.4 Assessing the Quality of the Balance

The overarching aim of the propensity score model is to balance the treatment cohorts on the measured covariates so that an unbiased treatment effect can be determined. One way to evaluate whether this goal has been achieved is to compare the distribution of the baseline covariates between the two treatment cohorts.

The standardized bias will be used as described in Yang and Dalton⁽¹⁴⁾ to assess the distance in marginal distributions of the covariates. For each covariate X it is defined as

the difference of the sample means before and after matching. For continuous variables the standardized bias before matching is given by:

$$\text{Standardized Bias} = \frac{(\bar{X}_1 - \bar{X}_2)}{\sqrt{0.5[V_1(X) + V_2(X)]}}$$

where $X_1 (V_1)$ is the mean (variance) in the treatment group and $X_2 (V_2)$ is the mean (variance) for the control group. The standardized bias will be calculated before and after matching.

For categorical variables with two levels, the standardized bias will be given by:

$$\text{Standardized Bias} = \frac{\hat{p}_1 - \hat{p}_2}{\sqrt{0.5[\hat{p}_1(1 - \hat{p}_1) + \hat{p}_2(1 - \hat{p}_2)]}}$$

where \hat{p}_1 and \hat{p}_2 denote the proportion or mean of the binary variable in the treatment and control group respectively. The standardized bias will be calculated before and after matching.

For categorical variables with more than two levels, a multivariate approach will be taken such that

$$T = (\hat{p}_{12}, \hat{p}_{13}, \dots, \hat{p}_{1K})'$$

$$C = (\hat{p}_{22}, \hat{p}_{23}, \dots, \hat{p}_{2K})'$$

where $\hat{p}_{jk} = \text{Pr}(\text{category } k \mid \text{treatment group } j)$ for $j=1$ or 2 and $k=1$ to K .

The standardized difference is given by:

$$\text{Standardized Bias} = \sqrt{(T - C)'S^{-1}(T - C)}$$

Where S is the covariance matrix defined as:

$$S = [S_{kl}] = \begin{cases} \frac{(\hat{p}_{1k}(1 - \hat{p}_{1k}) + \hat{p}_{2k}(1 - \hat{p}_{2k}))}{2}, & k = l \\ \frac{\hat{p}_{1k}\hat{p}_{1l} + \hat{p}_{2k}\hat{p}_{2l}}{2}, & k \neq l \end{cases}$$

Imbalance of covariates is defined as an absolute Standardized Bias greater than 0.2⁽¹⁵⁾.

Furthermore, differences in propensity scores for each matched pair (CZP minus comparator) will be calculated and presented as the number and percent of positive and negative differences.

If there is evidence of covariate imbalance after adjustment for PS quintiles, the propensity score model specification will be refined according to the iterative algorithm outlined in Section 8.1.2.2. The iterative process ends when the bias associated with observable baseline characteristics is either removed or reduced to a reasonable level. In the final analysis of the effect of treatment cohorts, a regression adjustment will be made for any covariate with residual imbalance after propensity score matching (Section 8.1.2.3).

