6.3 Determination of Sample Size

Prior to Amendment 5, the study planned for a total of 4000 patients (2000 patients per arm). A total of 3045 patients (1371 in the Cimzia Cohort and 1674 in the Comparison Cohort) were enrolled as of Mar 2017. The total duration of participation (treatment and follow-up) of 8 years is planned for each patient. Assuming an 8% annual drop-out rate (1) (withdrawal, lost-to-follow-up or death), approximately 25,000 (12,500 per arm) total patient years (p-y) post-enrollment is expected in this registry. With a two-sided significance level of 0.05, the study is designed to have at least 80% power to detect incidence rate ratios (calculated based on observed rates in the control group) of 1.5 for serious infections, 3.3 for lymphoma, and 1.56 for solid malignancies after 8 years. Event rate estimates for this study were calculated using corresponding event rates observed in a CD anti-TNF α registry study control group (1, 2).

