8 PRIMARY ANALYSES

The primary outcome of this observational study is malignancy (malignant tumors and malignant or unspecified tumors). However, in addition, the following list of AEs of interest will be

summarized using cumulative incidence (proportion) and incidence rate (events per 100 patient-years). These AEs are described in section 8.2.3 and defined in detail in the AE of interest – Cimzia Program 2018-01-05 document.

- Serious infections
- Opportunistic infections
- Serious cardiovascular events (also called major adverse cardiac events, or MACE)
- Congestive heart failure
- Demyelinating-like disorders
- Aplastic anemia, pancytopenia, thrombocytopenia, neutropenia and leucopenia
- Serious bleeding events
- Lupus and lupus-like illness
- Serious skin reactions

Although not officially AEs of interest, the following events will also be summarized as described in the AEs of Interest – Cimzia Program 2018-01-05 guidance document.

- Hepatic Events
- Hypersensitivity reactions and anaphylactic reactions

Separate from the AEs of interest document, malignant lymphomas, non-melanoma skin cancer, and autoimmune disorders will also be summarized.

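### In the propensity-score-matched analysis, age may differ by up to 0.2 SD between cohorts without adjustment, although malignancy is the primary outcome

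*SAP*

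**What the plan says.** The SAP matches Cimzia and comparator patients 1:1 on the propensity score, checks covariate balance, and adjusts for what remains unbalanced.

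- **Balance limit (SAP 8.1.2.4):** "Imbalance of covariates is defined as an absolute Standardized Bias greater than 0.2". The reference given for 0.2 is, by its title, a text on statistical power analysis. No other numeric limit appears; 8.1.2.3 and 8.1.2.4 otherwise speak only of reasonable limits or a reasonable level.
- **What is adjusted (SAP 8.1.2.4):** "a regression adjustment will be made for any covariate with residual imbalance after propensity score matching".
- **For which outcome (SAP 8.1.2.3):** variables that still differ are controlled for in the model of "the effect of treatment cohorts on the risk of serious infections". Malignancy is not mentioned there.
- **Primary outcome (SAP 8):** "The primary outcome of this observational study is malignancy".
- **Time-to-event analysis (SAP 8.1.3):** hazard ratios, confidence intervals and exploratory p-values are planned, but no covariates are named.
- **Rate comparison (SAP 8.1.4):** the text asks for cohort effects given every covariate in Section 4.1, which includes age. The sample code beside it, labelled as potential code, has COHORT as its only model term.
- **Secondary regression (SAP 8.1.5):** a conventional regression uses the full propensity-score covariate vector as a robustness check.

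**The concern.** The bias from a residual imbalance depends on two things: how large the imbalance is, and how strongly the covariate predicts the outcome. A single cut-off looks only at the first. A gap of 0.19 SD in a weak predictor may be harmless. The same gap in age, on a cancer outcome, may not be. Under 8.1.2.4 both are called balanced and neither is adjusted for in the matched analysis.

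The matching steps do not themselves bound the age gap. The caliper limits distance on the score: "the size of the caliper will be set to a quarter of a standard deviation of the logit of the propensity score". The Mahalanobis step in 8.1.2.3 uses a smaller set of key covariates that are not named, so age need not be among them.

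At stake is the matched malignancy estimate in a post-approval safety study. An older Cimzia cohort would push the rate ratio up, and a younger one would push it down and could hide a signal. Because 8.1.2.3 ties residual adjustment to serious infections, it is also unclear whether a covariate that does exceed 0.2 would be adjusted for in a malignancy model.

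**Working it through.** The 0.2 is a convention, so there is no calculated figure to reproduce. The check asks what it allows.

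**Inputs from the documents**
- Limit on standardized bias: 0.2 (SAP 8.1.2.4).
- Unit: "For continuous variables the standardized bias before matching is given by" the difference in means over sqrt(0.5[V1 + V2]), and the bias is calculated both before and after matching. The unit is therefore the pooled SD.
- Age is in the covariate list and "Characteristics that are continuous will remain as such" (SAP 4.1).
- Scale for comparison: Protocol 6.3 gives detectable rate ratios of "1.5 for serious infections, 3.3 for lymphoma, and 1.56 for solid malignancies after 8 years". SAP 2.4 gives the same ratios after 10 years. The 1.56 serves here only as a yardstick.

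**Assumed, because the documents do not give them**
- Age SD: 12 to 16 years.
- Log-rate slope b of malignancy on age: 0.03 to 0.09 per year, roughly 3 to 9% per year.
- A log-linear age effect, similar age spread in both cohorts, and no drug effect.

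**Step 1. Largest age gap that counts as balanced** = 0.2 × SD.
- SD 12: 0.2 × 12 = 2.4 years
- SD 15: 0.2 × 15 = 3.0 years
- SD 16: 0.2 × 16 = 3.2 years

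**Step 2. Rate ratio produced by that gap alone** = exp(b × gap).

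| b per year | SD 12 (2.4 y) | SD 15 (3.0 y) | SD 16 (3.2 y) |
|---|---|---|---|
| 0.03 | 1.07 | 1.09 | 1.10 |
| 0.05 | 1.13 | 1.16 | 1.17 |
| 0.07 | 1.18 | 1.23 | 1.25 |
| 0.09 | 1.24 | 1.31 | 1.33 |

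**Step 3. Share of the yardstick on the log scale.** ln(1.56) = 0.445. The smallest case is 0.03 × 2.4 = 0.072, and 0.072 / 0.445 = 16%. The largest is 0.09 × 3.2 = 0.288, and 0.288 / 0.445 = 65%.

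**Step 4. Is 0.2 within chance?** The standard error of the standardized bias is about sqrt(2/n) for n pairs. With all 1371 Cimzia patients (enrolled as of March 2017) matched, it is 0.038, so 0.2 is 5.2 standard errors. With an assumed 800 pairs it is 0.050, so 0.2 is 4.0 standard errors. The limit allows much more than chance imbalance.

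**Step 5. Binary covariates.** Solving the SAP's two-level formula for a bias of 0.2 gives 20% versus 28.5%, or 50% versus 59.9%. Prior use of a drug class could differ by 8 to 10 percentage points and still count as balanced.

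**Step 6. A limit of 0.1.** The log-scale bias halves: exp(0.036) = 1.04 to exp(0.144) = 1.15. A stricter limit shrinks the problem but does not remove it.

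**The case against.** The strongest reply is that the plan does adjust for age. The text of 8.1.4 conditions the Poisson cohort effect on all Section 4.1 covariates, and those include age and all three prior-treatment variables. Section 8.1.5 adds a full-covariate regression. This stands: a reader might infer that age goes unadjusted throughout, and the documents do not support that. What remains is that the 8.1.4 code contradicts its text, that 8.1.5 is secondary, and that neither is the matched analysis. The SAP warns that 8.1.5 may be hard to interpret if the cohorts differ substantially, and that is when readers would lean on the matched result.

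Second, 0.2 SD is a tolerance. Age is in the score model, a caliper applies, and the score model is to be refined until balance is acceptable. This also stands. Nothing in the documents suggests that a gap near 3 years is likely.

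Third, the age SD and the cancer slope both come from outside the documents, and at the low end the distortion is only 1.07. True, which is why a range is given.

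Fourth, the SAP calls its analyses descriptive. That lowers the stakes but does not remove the bias, because confounding shifts an estimate whether or not it is tested.

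Finally, nothing in the documents favours 0.1 over 0.2, and any uniform cut-off ignores how strongly a covariate predicts the outcome. This is accepted, so the recommendation does not rest on a different cut-off.

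**Conclusion.** The point holds for the matched analysis only. There, 8.1.2.4 lets age differ by up to 0.2 SD without adjustment: 2.4 to 3.2 years if the age SD is 12 to 16. With an assumed rise in malignancy of about 3 to 9% per year of age, that maximum gap gives a rate ratio of about 1.07 to 1.33 in the absence of any drug effect. Against 1.56 this is a modest distortion. A reader might infer a bias as large as the effect the study was sized to detect, but even the worst corner of the assumed range reaches only 65% of it on the log scale.

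A related gap needs no assumptions. The SAP does not write out a matched outcome model for malignancy: 8.1.2.3 names serious infections only, 8.1.3 names no covariates, and the code in 8.1.4 does not match its text. The change is worth making because the bias is avoidable, concerns the primary outcome, and can be removed with variables already collected.

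**What to change.** 1. In SAP 8.1.2.4, state that the matched outcome models for malignancy and for serious infections always include continuous age and prior biologic, immunosuppressant and corticosteroid use, whatever the balance table shows, plus any other covariate flagged as imbalanced.
2. In SAP 8.1.2.3, extend the adjustment for persisting differences to malignancy.
3. In SAP 8.1.4, make the sample code carry the Section 4.1 covariates that the text requires.
4. Optionally, lower the limit to 0.1. Once age is always in the model, its adjustment no longer depends on the cut-off.

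The cost is SAP wording and a few model terms. All four covariates are already in the Section 4.1 list, so no new data are needed. The downside is a few degrees of freedom; the optional stricter limit might also need another round of score refinement.
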